Intervention arm. Within one week of completion of *MC1R* genotyping (approximately 1-3 weeks after signing informed consent), a risk and prevention packet will be mailed to each participant randomized to the intervention group. These printed materials will highlight information about natural variation in *MC1R* and its role in the development of melanoma, and they will contain personalized information about melanoma, melanoma risk and melanoma prevention (i.e. sun protection and skin examination). These materials also will include information about sun protection behaviors targeted to children. Within two weeks of receipt of the risk and prevention mailed packet, the study health educator will contact each participant by telephone allowing the opportunity for a supplementary interactive personalized educational session. This procedure of mailed receipt of genotype results with follow-up via telephone by a health educator has previously been demonstrated as a feasible and acceptable method for dissemination of information specific to low penetrance genetic testing ([McBride et al. 2002](#)). Subsequent to the telephone session with the health educator, all participants in the intervention group will receive a summary letter from the research team to reinforce information

contained in the original risk and prevention packet and/or covered during the health education telephone session. This letter may include detailed information about specific inherited *MC1R* variants if requested by the participant during the telephone health education session. This letter will include the targeted date range for completion of the 6 and 12 month follow-up questionnaires. For our H/L population this letter will include the targeted date range for completion of 3 and 9 month follow-up questionnaires. All participants in the intervention group (our white, non-Hispanic and our H/L populations) will receive a second summary letter from the research team to reinforce information contained in the original risk and prevention packet and/or covered during the telephone health education session upon completion of their final questionnaire (12 month follow-up survey for our white, non-Hispanic participants and 9 month follow-up survey for our H/L participants) along with the mailing of their final compensation gift card after study completion. Electronic communication modalities such as e-mail will be made available to participants as requested.

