Biospecimen collection and baseline questionnaire. Once the patient provides informed consent, he/she will provide a saliva sample for isolation of genomic DNA. Oragene® (DNA Genotek, Inc.) kits will be used for saliva collection, and saliva samples will be delivered to the Moffitt Tissue Core for processing.

MC1R genotyping. Saliva samples will be processed for the isolation of genomic DNA in the Moffitt Tissue Core according to the manufacturer's instructions. Isolated DNA will be delivered to the Moffitt Molecular Genomics Core for complete exonic sequencing of *MC1R* (1 exon, 961 bp) to identify all existing variants using published methods ([name] et al. 2010). [name] has vast experience with sequencing this locus, having genotyped and interpreted *MC1R* sequencing output for over 5000 samples ([name] et al. 2006, [name] et al. 2010).

Using observed *MC1R* genotypes, we will identify our target high (genetic) risk population based on criteria set forth in our previous work ([name] et al. 2010). We will define a high risk *MC1R* variant as any of the following: p.D84E, p.R151C, p.D160W, and p.D294H. We also consider the g.86_87insA, g.411delC, and g.537_538insC insertion/deletion variants, the p.Y152X and p.R163X nonsense variants as high risk based on their effect (premature truncation) on the receptor protein, although we anticipate observing only a handful of these variants given their low prevalence in the general population ([name] et al. 2006). Low risk *MC1R* variants include any other observed non-synonymous variation distinct from those variants listed above. Consistent with our prior findings, we define the high risk group as persons who carry at least one high risk *MC1R* variant or two low risk variants (in the absence of a high risk variant) ([name] et al. 2010). We define the low risk group persons who carry only one low risk or no *MC1R* variant (i.e. all remaining individuals).

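### The list defining high-risk MC1R genotypes contains p.D160W, very probably a wrong entry; applied literally, it would class carriers of one copy of the intended variant and no other as low risk

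*Combined protocol and SAP*

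**What the plan says.** The variant list appears once, in the GENETIC TESTING section under MC1R genotyping. The high-risk population is to be identified "based on criteria set forth in our previous work". The section then restates the criteria and defines a high-risk variant "as any of the following: p.D84E, p.R151C, p.D160W, and p.D294H". It adds three insertion/deletion variants and "the p.Y152X and p.R163X nonsense variants as high risk based on their effect (premature truncation) on the receptor protein". Low-risk variants are "any other observed non-synonymous variation distinct from those variants listed above".

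The group rule follows. The high-risk group is anyone with at least one high-risk variant "or two low risk variants (in the absence of a high risk variant"). The low-risk group is "persons who carry only one low risk or no" variant. The assay sequences the whole exon, so any change at codon 160 would be seen and then sorted by this rule.

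The resulting groups are the randomisation strata: 500 high risk and 500 low risk in the white, non-Hispanic trial, with 250 per arm in each. The Hispanic/Latino trial also stratifies on MC1R risk, and no separate definition is given for it. Intervention-arm packets are personalised: "they will contain personalized information about melanoma, melanoma risk and melanoma prevention". Consented people who are not selected are told their risk status by letter. Placebo participants are given genotype and associated risk at the end of the study (RISKS). Participants in the Hispanic pilot receive no results.

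**The concern.** The four named missense variants decide who is high risk, and one of them looks wrong on its face. The default clause gives no protection against an error in the list, because a variant that is misnamed becomes an unlisted variant and so counts as low risk.

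Three things would be at stake if the printed list were applied:

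- **The low-risk stratum.** The Randomization section uses it to look for harm from a 'negative' result. It would include people whom the investigators meant to call high risk.
- **Recruitment.** People who should count towards the high-risk target would not.
- **Feedback.** Some participants would be told that their risk is low when the intended classification says otherwise.

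**Working it through.** No sample-size or power figure in the plan depends on this entry, so there is no stated figure to reproduce. The check has four steps.

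**1. Is the entry plausible?** Inputs are the substitutions as printed and the standard genetic code.

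| Entry | Codons before | Codons after | Minimum base changes |
|---|---|---|---|
| D84E | GAT, GAC | GAA, GAG | 1 |
| R151C | CGT, CGC, CGA, CGG, AGA, AGG | TGT, TGC | 1 |
| D160W | GAT, GAC | TGG | 3 |
| D294H | GAT, GAC | CAT, CAC | 1 |
| Y152X | TAT, TAC | TAA, TAG, TGA | 1 |
| R163X | CGT, CGC, CGA, CGG, AGA, AGG | TAA, TAG, TGA | 1 |

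For D160W, GAT to TGG changes G to T, A to G and T to G; starting from GAC, the third change is C to G. Tryptophan is one base from arginine, glycine, leucine, serine, cysteine or a stop codon. It is never one base from aspartate.

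**2. Who would change group?** Suppose the intended variant is a real codon-160 change that the list misnames. The printed rule then treats it as one low-risk variant. Two copies are counted here as two variants.

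| Carrier's genotype | Printed rule | Intended rule |
|---|---|---|
| One copy, nothing else | Low | High |
| One copy plus one low-risk variant | High | High |
| Two copies | High | High |
| One copy plus a listed high-risk variant | High | High |

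Only the first row moves, and it moves from high to low. Nobody moves into the high-risk group.

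**3. What does that do to the comparisons?** Everyone in the high-risk stratum would still meet the intended definition, and arms are randomised within it. The 500 are drawn from people classed as high risk, so the numbers behind the stated power stay at 250 per arm. The cost is more screening to reach 500, and a stratum without single-variant carriers of the codon-160 change. In the low-risk stratum the arms are also randomised, but the people described would be a mixture.

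**4. How many?** The documents give no variant frequencies. For scale only, let q be the assumed allele frequency of the codon-160 variant, h that of other high-risk variants and l that of low-risk variants. Assume Hardy-Weinberg proportions and at most one variant per chromosome, so w = 1 − q − h − l is the frequency of chromosomes with none.

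- Moved = 2qw
- Intended high risk = 1 − (w² + 2wl)
- All carriers = 1 − (1 − q)²

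The assumed values are q from 0.01 to 0.08, h of 0.05 or 0.10, and l of 0.10 or 0.20.

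- Fewest moved (q = 0.01, h = 0.10, l = 0.20): w = 0.69; moved = 2 × 0.01 × 0.69 = 0.0138, or about 17 of 1200 enrolled. Intended high risk = 1 − (0.4761 + 0.2760) = 0.248, so 6% of that group moves.
- Most moved (q = 0.08, h = 0.05, l = 0.10): w = 0.77; moved = 2 × 0.08 × 0.77 = 0.1232, or about 148 of 1200. Intended high risk = 1 − (0.5929 + 0.1540) = 0.253, so 49% of that group moves.

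Across the grid, 65% to 84% of carriers move, and they make up about 2% to 15% of the printed-rule low-risk group. The grid is not calibrated to this trial. It gives an intended high-risk share of 13% to 37%, whereas filling both quotas of 500 from 1200 enrolled needs a share between 500/1200 = 42% and 700/1200 = 58%. The range is therefore not an estimate.

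**The case against.** The strongest reply is that the printed list only summarises a classification that already exists. The section refers to criteria from the investigators' earlier work, and the Hispanic recruitment text describes an established genotyping pipeline already operating in this protocol. The laboratory may never have used the printed entry, in which case nobody was misclassified. This stands: the documents do not show that any participant was affected. It does not defend the text, because the protocol states the list as its own definition and the documents contain no other.

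A reader might infer more than the documents support in four ways:

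- **That all carriers of the intended variant become low risk and are told so.** Only those with one copy and no other non-synonymous variant move. Placebo participants learn their result only at study end, and pilot participants never do.
- **That the primary results are biased or underpowered.** The error only removes people from the high-risk stratum. It does not disturb randomisation within that stratum or the 500 to be randomised.
- **That the correct entry is p.R160W.** The codon argument shows that the printed entry is anomalous, but not which part is wrong. The reference residue, the position or the substituted residue could each be mistyped. The documents give neither the reference residue at codon 160 nor the cited list.
- **That a definite number were misclassified.** Assuming that 10% to 30% of a fixed 500 are affected gives 50 to 150, but the share has no source. The 500 is a quota filled by screening, and not every person classed as low risk is randomised.

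**Conclusion.** The point holds in a limited form. p.D160W is very probably a wrong entry in the only list of high-risk variants in the documents. A three-base change is not strictly impossible, but it is out of line with every other substitution listed.

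If the list was applied as printed, and the intended variant is a codon-160 change, one genotype class would be misplaced. The effects would be a mixed low-risk stratum, lower high-risk yield, and wrong risk feedback to affected intervention-arm and non-selected participants during the study and to affected placebo participants at its end. If the pipeline used the correct criteria, this is an error of text only. The sponsor can establish which; the documents cannot.

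The number affected cannot be derived. The illustrative 17 to 148 of 1200 rests wholly on assumed frequencies. The point still deserves action because the list decides both stratum membership and what people are told about their genetic risk.

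**What to change.** 1. Check the p.D160W entry against the cited prior classification and the reference sequence that the pipeline uses, and correct it under MC1R genotyping. p.R160W is a likely reading, to be confirmed and not assumed.
2. Confirm that the genotype-calling table and the feedback materials use the corrected entry, in both the white, non-Hispanic and the Hispanic/Latino trials.
3. If anyone was classified on the printed entry, reclassify from the stored sequence, and report how many changed group and what feedback they had received.

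The cost is a correction to one entry and a small amount of checking. It needs no new samples or participants and no change to the sample size.
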